Data and Safety Monitoring Plan: The Principal Investigator (PI) at the Colorado site will monitor data and safety and be responsible for promptly reporting any related protocol concerns, including Serious Adverse Events (SAEs) and Adverse Events (AEs), to the Research Participant Advocate and to COMIRB. The Maine site and Maine Health IRB will rely on the COMIRB for review, approval, and ongoing regulatory oversight of the study. The PI at the Maine site will monitor study conduct at the site, monitor data and safety, and will be responsible for promptly reporting concerns, SAE and AE to the Colorado lead PI and to COMIRB as the reviewing IRB of record. The Principal Investigator at the Colorado and Maine subcontract site have no conflicts of interest (financial, academic, professional) that might interfere with being responsible for data and safety monitoring. The data will be examined in the course of the protocol on at least a monthly basis by the Principal Investigator at the Colorado and Maine subcontract site. Access to the database will be restricted to study personnel and standard conventions to protect the security of the database will be observed. Additionally, the PI (Colorado site) and subcontract PI (ME) will report any SAEs for this study that might include a child falling from the horse or the possibility of injury to one of the study personnel during the evaluations or treatments. The Principal Investigator (CO) and subcontract PI (ME) will also routinely communicate with the study personnel at their respective sites (Colorado and Maine) regarding the occurrence of any SAEs and be responsible for immediately communicating this information to their respective IRB Research Subject Advocate.

Study data will be collected and managed using REDCap (Research Electronic Data Capture).¹³¹ REDCap is a secure web application designed to support data capture for research studies, providing user-friendly web-based case report forms, real-time data entry validation (e.g. for data types and range checks), audit trails and a de-identified data export mechanism to common statistical packages (SPSS, SAS, Stata, R/S-Plus). The REDCap system was developed by a multi-institutional consortium which includes University of Colorado–Denver and was initiated at Vanderbilt University. The database is hosted at the University of Colorado–Denver Development and Informatics Service Center (DISC), which will be used as a central location for data processing and management. REDCap data collection projects rely on a thorough study-specific data dictionary defined in an iterative self-documenting process by all members of the

research team with planning assistance from the DISC. This iterative development and testing process results in a well-planned data collection strategy for individual studies. REDCap also includes a powerful tool for building and managing online surveys. The research team can create and design surveys in a web browser and engage potential respondents using a variety of notification methods. REDCap is flexible enough to be used for a variety of types of research and provides an intuitive user interface for database and survey design and data entry.

The study database for this multisite study will be housed at CU Denver, and access to the study database will be monitored and controlled by the study PI at the Colorado site. All study users will be required to complete applicable training to gain access and will each have a unique logon and password. The data will be backed up daily. There will be an audit trail of users and changes to the data. Maine site's, physiological data (EDA, HR, HRV) will be stored and managed through OpenText, a secure, online, data sharing platform.

Data Analysis Plan:

Data Sharing Plan: Study data will be collected and managed using REDCap electronic data capture tools hosted at the University of Colorado.¹³¹ REDCap (Research Electronic Data Capture) is a secure, web-based application designed to support data capture for research studies, providing: (1) an intuitive interface for validated data entry; (2) audit trails for tracking data manipulation and export procedures; (3) automated export procedures for seamless data downloads to common statistical packages; and (4) procedures for importing data from external sources

Physiological data (HR, HRV, EDA) will be monitored on an ongoing basis for quality control throughout the study by physiological activity assessment experts, both visually and using automated quality control software.¹³² Video recordings of 20% of each 10-week intervention will be shared with the intervention fidelity coordinators to rate intervention fidelity. Colorado's site physiological and fidelity video data will be shared through the CU One Drive and Maine site's physiological and fidelity video data will be shared through OpenText. Fidelity videos may also be shared via flash drive mailed via FedEx.

Data auditing and cleaning: HRV: Following the authoritative guidelines given in the Task Force,¹³³ data will be band-passed filtered (0.5-45Hz), heartbeats will be detected by automatic multiscale-based peak detection,¹³⁴ and lost data and/or premature atrial/ventricular contractions corrected via cubic spline interpolation. Time-domain indices (HR; SD; root-mean square of successive differences, RMSSD) will be calculated per standard methods. Frequency-domain indices (LF, low-frequency power; HF, high-frequency power) will be calculated via Lomb-Scargle Periodogram, and reported as natural log values. Standard covariates will be applied, and data quality reporting indices will be reported.^{135,136} EDA will be decomposed into tonic and phasic activity using standard methods⁴⁰ and de-noised depending on the accelerometer data – periods of high physical activity will be removed from the analysis period. The mean, SD, and non-specific skin conductance responses (NSSCRs; bursts of activity over 0.2uS) will be extracted per time period. NSSCRs will be reported as depolarizations per minute. Signal quality for both physiological records, which is frequently problematic during ambulatory recording, will be maintained through the combined use of automated tools for quality control,¹³² visual artifact identification, and redaction.¹³⁷

During each 10-week intervention (THR and BA), [name] lab team will meet with study PI, [name] and RAs from Colorado and Maine sites to monitor the Shimmer ECG (HR/HRV) and EDA data collected for quality and for possible equipment failure issues. [name] lab team in collaboration with [name] will then determine which data points collected will be used for analyses, ensuring that each subject has a beginning point (Lesson 1 or alternate lesson 2 or 3), midpoint (Lesson 6 or alternate lesson 7), and endpoint = (Lesson 10 or alternate lesson 9 or 8).

General consideration of statistical analysis: Prior to the start of any formal analyses, data for each variable will be examined to identify unusual values that need to be queried, including outliers, patterns of missing values, and non-Gaussian distributions (i.e., have significant skewness and kurtosis). Baseline demographic and clinical characteristics will be summarized using descriptive statistics and grouped by intervention arms. Between-arm difference in demography and baseline variables will be examined using t-test or chi square test respectively for continuous and categorical variables. Any imbalance that could potentially be a confounding factor for the outcome will be adjusted for in statistical models (see below). The primary efficacy analysis will use the “intent-to-treat (ITT)” principle to test our study hypotheses under practical and realistic conditions where not all participants follow or complete the program. All randomized participants will be analyzed in the ITT analyses. Linear Mixed Effect Model (LMM) will serve as the primary method to handle missing values. Other analyses such as completer analysis and analyses with imputed data will be deemed as sensitivity analysis for efficacy examination. However, for mediation analysis, only participants with both the

mediator (intervening) variable and outcome variables available will be included to explore mechanism of the intervention effect. No interim analysis will be conducted. In all analyses, a $p \leq 0.05$ will be considered significant. SAS and Mplus software will be used for these analyses.

AIM1: Efficacy assessment (for H1a-1c): LMM with unstructured covariance will be used to model baseline and end of treatment (EoT or T_2) primary and secondary outcome measures as well as expanded outcomes where fixed effects include evaluation time (baseline or EoT) and intervention arm indicator (THR/BA), as well as their interaction.

[figure not shown]
Estimate of the interaction will be used to quantify effect size and tested for statistical significance.

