
The objective of this proposed RCT is to identify physiological mediators of our well-tested^{13,15} 10-week manualized¹⁶ THR intervention compared to a similarly structured BA control group in up to 250 youth ages 6-16 yrs. with ASD and co-occurring psychiatric disorders recruited from the community, outpatient clinics, and a psychiatric hospital setting. An additional 20 ASD youth with co-occurring psychiatric disorders will be recruited for the exploratory aim's waitlist control and Hybrid intervention groups.

Specific Aim 1: Examine physiological mediators in a THR intervention group compared to a BA control on multivariate outcomes by measuring individual physiological response profiles and analyzing them for predictive validity and mediating effects on primary (irritability, hyperactivity), secondary (social communication, social cognition, and word fluency) and expanded outcomes (emotional dysregulation, caregiver QOL, and crisis mental health care usage).

Hypothesis 1a (H1a). *THR group will have significantly greater improvement in outcomes collected at baseline compared to post-intervention. H1b: Post-intervention (week 10) afternoon salivary cortisol levels will be significantly reduced (indicating less stress) in the THR group compared to baseline/week one levels. H1c. THR group will have a decrease in heart rate and electrodermal activity and an increase in heart rate variability, both indicating a calm state, from baseline to post- intervention. H1d. Physiological measures collected at intervention midpoint and post-intervention) will be correlated with and largely explain/mediate the effects of THR on post-intervention outcomes.*

Specific Aim 2: Evaluate the durability of Aim 1 outcomes in the THR group compared to the BA group control six-months post intervention period. *H2. THR group will maintain significantly greater outcome gains six-months after the intervention compared to the BA control.*

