Power analysis: Because significant intervention effect is the prerequisite of mediation analysis, this study is powered primarily on analyses of the primary outcome, ABC-C irritability. For the primary efficacy analysis at T2, effect sizes were estimated for the primary outcome (ABC-C irritability) based on data from our THR RCT¹³ among participants who had psychiatric diagnosis (N=27 for THR and N=26 for BA, data not published). The irritability score decreased by 6.9 (1.66 SEM) in the THR group and 2.3 (1.8 SEM) in the BA group, resulting in a Cohen's d of 0.62 for efficacy. We will enroll 142 participants (71 per arm). To allow for 20% attrition (which is 1% higher than that in our previous trial) at T₂, the sample size for completer or mediation analysis would be 56 per arm. In this case, we will have 97% power at 5% significance to detect significance of THR efficacy for ITT analysis (Aim1) and 90% power for completer analysis. For the mediation analysis, our previous data indicate that the standardized coefficient for the total effect (path c) is 0.34. There are no previous data available for estimating coefficients for paths a and b. We assume that both coefficients are of medium effect size¹³⁷ and the indirect path will explain half the total effect. That is, $a \times b = 0.17$ (e.g., $a=0.4$, $b=0.43$). In this case, a total sample size of 112 provides 90% power at 5% significance to detect a significant indirect effect. This power estimate is based on the Sobel test and was calculated by the R package, power Mediation. **Table 2** shows the power for analyzing secondary and exploratory outcomes at T₂ if the ES is similar to those from data in our previous RCT. (Based

TABLE 2		Power at 5% significance	
Power from ES	ITT (n=81/arm)	Completers (n=56/arm)	
ABC-C Irritability	97	90	
ABC-C Hyperactivity	94	83	
SRS Social Cogn.	92	80	
SRS Social Comm.	>99	>99	
SALT # diff. words used	>99	>99	
SALT # words used	>99	>99	

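### Aim 1 names two primary outcomes and the power section names one; with every test at 0.05 and no success rule, the two-sided error of the primary claim could reach 9.75% if either outcome suffices

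*Protocol*

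**What the plan says.** Three places in the protocol bear on the primary claim.

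- **Specific Aim 1** groups the outcomes as "primary (irritability, hyperactivity), secondary (social communication, social cognition, and word fluency", followed by a set of expanded outcomes. The two primary outcomes are not ranked.
- **Power analysis** states that "this study is powered primarily on analyses of the primary outcome, ABC-C irritability", in the singular. Hyperactivity appears there only as a row of Table 2, of which the text says that it "shows the power for analyzing secondary and exploratory outcomes at T₂". That description is loose, because irritability is also a row of the same table.
- **General consideration of statistical analysis** states: "In all analyses, a $p \leq 0.05$ will be considered significant". It also says "No interim analysis will be conducted", so repeated looks are not a second source of error.

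The Aim 1 efficacy paragraph fits the same mixed model to primary, secondary and expanded outcomes. For the time-by-arm term it says: "Estimate of the interaction will be used to quantify effect size and tested for statistical significance". The AIM 2 paragraph then takes forward whichever outcomes were significant in Aim 1, one by one.

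The protocol contains no order across outcomes, no adjusted threshold and no both-must-be-significant rule for Aim 1.

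**The concern.** Hyperactivity is primary in one section and apparently not primary in another. An analysis plan cannot follow both sections, so this has to be settled in the protocol.

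The labels decide what may be called a success. Under Specific Aim 1 and the 0.05 sentence as written, a trial that misses on irritability but reaches 0.05 on hyperactivity could be reported as positive on a primary outcome. Under the Power analysis it could not. With the labels unresolved, the choice could be made after the results are seen.

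The two outcomes can plausibly diverge. The protocol's account of the six-month follow-up pilot says that irritability reductions were maintained against the control and hyperactivity reductions were not. In the replication pilot the hyperactivity effect was the larger one (1.49 against 1.08).

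**Working it through.** **Inputs.** Two primary outcomes (Specific Aim 1) or one (Power analysis). Threshold 0.05 per test (General consideration). Effect size for irritability from the Power analysis: "resulting in a Cohen's d of 0.62 for efficacy". Enrolment: "We will enroll 142 participants (71 per arm" in the text, 81 per arm in the Table 2 header, and 56 per arm for completers. The documents give no correlation between the two outcomes, so the values below are assumptions.

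**Step 1: sidedness.** The protocol does not state it. A two-sample comparison with d = 0.62 and two-sided 0.05 gives 97.5% power at 81 per arm, 95.6% at 71 and 90.2% at 56. The protocol states 97% (ITT) and 90% (completers), so two-sided 0.05 reproduces its figures. One-sided 0.05 would give about 95% at 56 per arm and does not. (The ITT figure matches 81 per arm better than 71; that mismatch is a separate matter.)

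**Step 2: error if either outcome suffices, independent tests.**

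- Either direction: 1 − (1 − 0.05)² = 1 − 0.9025 = 9.75%.
- Favouring THR only, at 0.025 per test: 1 − (1 − 0.025)² = 1 − 0.950625 = 4.9%, against 2.5% for a single test.

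**Step 3: correlated tests.** With bivariate normal test statistics, the error in either direction is 1 − P(|Z₁| < 1.96 and |Z₂| < 1.96). The error favouring THR is 1 − P(Z₁ < 1.96 and Z₂ < 1.96), with positive Z favouring THR.

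| Assumed correlation | Either direction | Favouring THR only |
|---|---|---|
| 0 | 9.75% | 4.9% |
| 0.3 | 9.5% | 4.8% |
| 0.5 | 9.1% | 4.5% |
| 0.7 | 8.4% | 4.2% |
| 0.9 | 7.0% | 3.5% |
| 1 | 5.0% | 2.5% |

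For jointly normal statistics 9.75% is the maximum. The bound without any assumption is 0.05 + 0.05 = 10%.

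**Step 4: the other success rules.** If irritability alone is primary, the error is 5%. If both must be significant, a false claim needs a false result on at least one null outcome together with significance on the other, so the error is at most 5%. A fixed order with irritability first also holds 5%.

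**Step 5: effect on power.** With irritability tested first at 0.05, its power stays as stated, 97% and 90%. For comparison, keeping both as primary at 0.025 each would give irritability 95.3%, 92.2% and 84.2% at 81, 71 and 56 per arm. Hyperactivity would have about 90%, 85% and 75%, using d of about 0.555 back-solved from Table 2 (94% at 81 per arm, 83% at 56).

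**The case against.** The strongest reply is that the 0.05 sentence is only a generic threshold. It does not say that either outcome suffices, and it is compatible with adjusted p-values, a hierarchy or a both-required rule. Multiplicity detail is commonly left to a statistical analysis plan, which may exist here but is not shown. The Power analysis also reads naturally as making irritability the sole primary outcome, in which case the error is 5%. All of this stands against quoting 9.75% as the trial's error rate. None of it removes the contradiction in labels, which lies wholly within the protocol. The scope of the 0.05 sentence (all analyses) and the outcome-by-outcome carry-forward to Aim 2 lean towards the either-suffices reading without stating it.

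A second reply is that independence is implausible, because both outcomes are subscales of one checklist completed by one designated caregiver. That also stands: 9.75% is an upper figure and the correlated rows are more realistic. Hypothesis H1a is directional, so the relevant contrast may be about 5% against 2.5%. That is smaller in absolute terms but still up to a doubling.

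A reader might infer more than this. Three stronger readings are not supported:

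- **Pooling all six outcomes in Table 2** gives a larger error figure. But most of those are secondary, so a false result on one of them is not a false primary claim, and several come from the same instrument or language sample. Adjusting the remaining secondary outcomes is a matter of preference.
- **Inheritance by the later analyses** is not shown. For an outcome with no six-month effect, requiring significance in Aim 1 first cannot raise its unconditional error above the 5% of its own Aim 2 test. Mediation is described as exploring mechanism and has its own screening step on completers.
- **A positive hyperactivity result after a null irritability result** is not in itself a false positive, since hyperactivity may truly improve. The question there is which outcome may carry the primary claim.

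**Conclusion.** The concern holds as a contradiction in the definition of the primary outcome, combined with a stated threshold of 0.05 and no success rule. The consequence for error is conditional. It is up to 9.75% two-sided if either outcome can carry the claim and the tests are independent, and about 8.4% to 9.5% at assumed correlations of 0.7 to 0.3. In the direction favouring THR it is up to about 5% instead of 2.5%. It is at most 5% if irritability alone is primary or both are required. The protocol does not settle which of these applies. A flat statement that the false-positive rate is 9.75% would go beyond the text. The contradiction itself needs no assumption.

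**What to change.** Before any outcome analysis by arm:

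- In Specific Aim 1 and the Power analysis, name ABC-C irritability at T2 as the single primary outcome. It is the outcome on which the trial is powered.
- Name ABC-C hyperactivity as the first key secondary outcome, tested at 0.05 only if irritability is significant.
- Amend the 0.05 sentence in the general statistical section to state this order.

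Power for irritability does not change. The cost is that a confirmatory hyperactivity claim becomes conditional on irritability. Because the trial is well advanced (the protocol records the Maine site as closed from the end of 2023), re-labelling a named primary outcome needs a dated amendment that gives the reason and confirms that no outcome data by arm had been analysed. If the sponsor prefers to keep both outcomes as primary, the protocol should instead state the success rule; splitting alpha equally would cost the power shown in Step 5.

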Ambulatory cardiovascular response patterns to a canine-assisted activity in psychiatrically-hospitalized and diagnosed ASD youth. This pilot study investigated participants (ages 6-18yrs) with a mean ABC-C irritability score of 26.5 (SD=8.3), measuring their peripheral physiological responses via the wrist-worn E4 device¹⁰⁰ to a 10-minute canine and handler treatment condition (DOG) compared to a 10-minute novel toy and handler control condition (TOY)¹⁰¹. In both conditions, HR slowed overall ($\eta^2=0.237$; DOG, d=0.37, p=0.046; TOY, d=0.64, p=0.002) and HRV increased overall ($\eta^2=0.465$, DOG, d=0.38, p=0.08; TOY, d=0.64, p=0.003), consistent with increased cardiac parasympathetic modulation (i.e., reduced stress response). However, no interaction was observed (p=0.23, p=0.75) with improvements equivalent in both conditions. While n=41 participants returned data, repeated measures ANOVA requires four individual values per person, reducing the sample to n=15 observations overall (paired comparisons n=23 and n=25). **Conclusion:** *This pilot demonstrates the feasibility of collecting biosensor data in a similar sample to the proposed study, and the ability to observe reactivity in animal and non-animal conditions. This pilot highlights need for more robust methods of gathering peripheral physiological data and increasing sample size to achieve appropriate power to account for potential data loss, both of which are accounted for in the current proposal.*

Feasibility pilot of ambulatory cardiovascular and electrodermal activity monitoring in ASD youth during THR. We assessed the feasibility of ambulatory peripheral physiological data collection in ASD youth while engaged in THR lessons over five contiguous weeks at the two centers (Colorado & Maine) proposed in this project. Eight ASD youth (6-13 yrs.; mean age = 9.1 yrs; mean ABC-C irritability score=15.8 (SD=11.10); 75% with co-occurring psychiatric

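### H1b and H1c are worded as change within the THR arm, the model assigned to them tests THR against BA, and that model lists no physiological measure

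*Protocol*

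**What the plan says.** **Hypotheses (Protocol, Specific Aim 1).** H1b predicts that "afternoon salivary cortisol levels will be significantly reduced (indicating less stress) in the THR group compared to baseline/week one levels". H1c predicts that the "THR group will have a decrease in heart rate and electrodermal activity and an increase in heart rate variability, both indicating a calm state"; the change it refers to is pre- to post-intervention. Neither mentions the BA arm. The aim above them is comparative ("Examine physiological mediators in a THR intervention group compared to a BA control on multivariate outcomes"), and H2 names its comparator outright: "THR group will maintain significantly greater outcome gains six-months after the intervention compared to the BA control".

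**Assigned analysis (Data Analysis Plan).** The relevant paragraph opens "AIM1: Efficacy assessment (for H1a-1c): LMM with unstructured covariance will be used to model baseline and end of treatment". The measures modelled are "primary and secondary outcome measures as well as expanded outcomes". Fixed effects are time, arm (THR or BA) and their interaction, and the interaction is the term that is estimated and tested.

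**Repeat of H1c.** At the end of the mediation paragraph, inside the analysis plan, H1c appears again as a prediction about the THR group alone.

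**Pilot (Preliminary Studies, canine-assisted activity).** Heart rate fell and heart rate variability rose with both the dog and the toy, with no interaction and "with improvements equivalent in both conditions".

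**The concern.** BA is there to separate the effect of the horse from everything else that comes with ten weekly sessions. A hypothesis that refers only to the THR arm does not use that control. If arousal falls over ten weeks for reasons common to both arms, H1b and H1c are true as written, whatever the horse adds.

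The interaction test would guard against this if it clearly applied to physiology, but the paragraph that specifies it leaves physiology out of its list of measures. Someone reporting the trial could judge H1b and H1c by their own wording or by the paragraph heading and cite the protocol either way. The two routes can give opposite answers. At stake is whether a THR-only fall in arousal can be reported as confirming a prespecified hypothesis about THR.

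**Working it through.** **1. The texts side by side**

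| Place | Comparison | Measures | Times |
|---|---|---|---|
| Specific Aim 1, H1b | THR against its own earlier level | cortisol | week 1, week 10 |
| Specific Aim 1, H1c; repeated in the analysis plan | THR against its own earlier level | HR, EDA, HRV | baseline, post-intervention (week 10) |
| AIM1 efficacy model, headed for H1a to H1c | arm-by-time interaction | primary, secondary, expanded | baseline, T2 |
| Mediation path a | arm predicting the mediator | physiological mediators | T0 to T1 |

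Specific Aim 1 defines the listed outcomes: primary is irritability and hyperactivity; secondary is social communication, social cognition and word fluency; expanded is emotional dysregulation, caregiver quality of life and crisis care use. None is physiological. The T0 and T2 assessment sections list no physiology either; it is filed under Time 1, as mediator assessments. So the model names no physiological variable at either of its time points.

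Path a is a between-arm test, but on the T0-to-T1 change, and the Time 1 label spans weeks 1, midpoint and 10 without singling out week 10. It is run only for outcomes significant on path c, and in completers. It does not replace a week-1-to-week-10 test.

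**2. The plan's own power figure**

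The protocol gives no power for H1b or H1c. For irritability it states 90% with 56 completers per arm and d = 0.62. Two-sample t, two-sided 5%: noncentrality = d√(n/2) = 0.62 × √28 = 3.28 on 110 df, power 90.2%. The figure reproduces.

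**3. Illustration: equal change in both arms, no effect of the horse**

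Inputs:
- 56 completers per arm (Power analysis).
- About 85% usable recordings (feasibility pilot): 56 × 0.85 = 47.6, taken as 48.
- d = 0.37 (heart rate, dog) to 0.64 (heart rate, toy), from the canine pilot. Using these as standardised paired changes over ten weeks is an assumption.
- Significance level 0.05, taken as two-sided.

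THR-only paired t-test, noncentrality = d√n on n − 1 df:

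| Shared d | n | Noncentrality | THR-only test significant |
|---|---|---|---|
| 0.37 | 56 | 0.37 × 7.48 = 2.77 | 77.6% |
| 0.64 | 56 | 0.64 × 7.48 = 4.79 | 99.7% |
| 0.37 | 48 | 0.37 × 6.93 = 2.56 | 70.9% |
| 0.64 | 48 | 0.64 × 6.93 = 4.43 | 99.1% |

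Between-arm test of change: the true difference is d − d = 0, so it rejects at the nominal 5%. A simulation of 20,000 trials with 56 per arm gave 4.9% (d = 0.37) and 5.1% (d = 0.64).

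A smaller shared change still matters: at d = 0.2 the THR-only test is significant in 27% (n = 48) to 31% (n = 56) of trials.

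**4. Scale of the pilot's d**

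Read as a paired standardised change, d = 0.37 would give p = 0.09 with 23 pairs or 0.08 with 25, not the printed 0.046, so the printed d may be on another scale. Working back from the heart-rate p-values (0.046 and 0.002) as t/√n gives about 0.42 to 0.73. The range used above is therefore not inflated for that pilot.

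**The case against.** The strongest reply is that the protocol already assigns these hypotheses a between-arm test. The efficacy paragraph is headed for H1a to H1c, and H1b and H1c concern only physiological variables, so the heading can hardly mean anything else. Aim 1 supplies BA as comparator for everything beneath it, and an incomplete list of dependent variables is a drafting gap that a statistical analysis plan may close. On this view the 78% to over 99% describes a test that nobody plans.

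Much of this stands. No analysis section describes a THR-only paired test. A reader might infer that the protocol has no between-arm test for physiology and that H1b and H1c will be declared met with no effect of the horse; the efficacy heading and its interaction term do not support that.

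A reader might also infer that the mechanism claim in H1d rests on the within-arm result. It does not: path a compares arms, so a change shared equally produces no arm effect there. Nor is week 1 the first exposure to setting and devices. Tolerance of the equipment is addressed at Visit I. Visit II is a 45-minute riding-center screening with saliva and monitor practice and, for THR children, a 10-minute mounted activity.

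The pilot is narrow. It compared single 10-minute dog and toy conditions, reported heart rate and its variability only, had p = 0.08 for variability with the dog, and retained 15 participants in the ANOVA. It says nothing direct about cortisol, EDA or change over ten weeks. The small THR-versus-BA cortisol pilot (8 per arm) reported no significant THR effect on cortisol.

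What the reply does not remove is the conflict in the text. H1b is not shorthand with the comparator left out: it states a comparator, the arm's own week-one level, and predicts a significant reduction against it. H1c is repeated in within-arm form inside the analysis plan. The heading points one way and the list of measures another.

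**Conclusion.** The point holds as a mismatch between hypothesis and test, together with an incomplete model specification. H1b and H1c are worded within the THR arm; the model assigned to them tests THR against BA but names no physiological measure; and path a covers only the T0-to-T1 change. As literally worded, both hypotheses could be called met by a change shared with BA.

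The figures (about 78% to over 99% for a THR-only test with 56 completers, 71% to 99% with 48, against 5% for the interaction) show how far the two readings can diverge. They do not forecast the trial. They rest on three assumptions: equal change in both arms, the pilot's d used as a paired standardised change, and that size carried from a 10-minute canine session to ten weeks. They have no direct bearing on cortisol or EDA. The textual conflict depends on none of these assumptions.

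**What to change.** - In Specific Aim 1, and where H1c is repeated in the analysis plan, restate H1b and H1c as a greater change from week 1 to week 10 in THR than in BA: a larger fall for cortisol, heart rate and electrodermal activity, and a larger rise for heart rate variability.
- In the AIM1 efficacy paragraph, name cortisol, HR, HRV and EDA at week 1 and week 10 as dependent variables of the model.
- State that H1b and H1c are judged on the arm-by-time interaction, and that change within the THR arm is reported descriptively.

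The cost is wording only, since BA physiology is already collected on the same schedule as in THR. The downside is that a between-arm test is harder to pass than a pre-post test, and the protocol gives no power for it on these measures.
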